7.4.3 BPI-SF variables

Pain Severity Score = Mean of items 3-6 (pain at its worst, pain at its least, average).

Pain Interference Score = Mean of items 9A-9G (interference of pain with: general activity, mood, walking, normal work, relations, sleep, enjoyment of life)

7.5 Subject Disposition

Subject disposition will be summarized as follows:

- The number of subjects that were screened, number that failed screening, and number in each analysis set will be summarized by treatment period and overall using the Screened Population.

- The number of early discontinuations and the reasons for withdrawals will be summarized by treatment period (T1/T2) and overall (T1 and T2) for the Safety Analysis population.
- The number of subjects who complete each treatment period of the study and the number of subjects present at each scheduled visit will be summarized by treatment period for the Safety Analysis population.

7.6 Protocol Deviations

Protocol deviations will be adjudicated into major and minor. A listing of both major and minor protocol deviations will be provided.

7.7 Baseline Comparability

Demographics and baseline characteristics will be assessed in a descriptive manner, and no formal statistical testing will be performed.

Standard continuous or categorical variable summaries will be presented for all subjects for the following variables based on the Safety Analysis population.

7.8 Demographic data

The following demographic variables will be summarized for all subjects: Age (years), gender, childbearing potential, race, ethnicity, height (cm), weight (kg), BMI (kg/m²), Straight leg raise, Femoral stretch test, Hepatitis B Surface Antigen, Hepatitis C Virus Antibodies, HIV-1 Antibody, and HIV-2 Antibody.

7.9 Medical History

Summaries of previous and ongoing conditions at screening will be presented. Conditions will be presented by Medical Dictionary of Regulated Activities (MedDRA) primary system organ class and preferred term.

7.10 Prior and Concomitant Medications

Prior medications are defined as all medications starting and ending before the first dose of study drug. Prior medications will be summarized for all subjects. Concomitant medications are defined as medications taken on or after the date of the index injection through the EOS/ET participation. Concomitant medications will be summarized by treatment period (T1/T2) using ATC Level 2 and listed. If the onset date of a concomitant medication is on or post the index injection dosing date but before the repeat injection dosing date, it will be considered as occurring during T1; otherwise,

the onset date of concomitant medication on or post the repeat injection date will be considered as occurring in T2. If a medication is taken during both treatment periods it will be counted in both periods.

7.11 Pharmacodynamic Analyses

All comparisons between treatments will be analyzed in log scale but will be reported as ratios with 90% confidence intervals for the difference. All PD analyses will use the PD Analysis population as the primary analysis population.

7.11.1 Dexamethasone-induced HPA suppression

Blood samples for PD will be collected at screening, for T1 at pre-dose (baseline), Days 1, 2, 3, 4, 5, 8, 15, and 28, for T2 at pre-dose (baseline), Days 1, 2, 3, 4, 5, 8, 15 and 28.

Dexamethasone-induced HPA suppression will be evaluated by using the observed plasma cortisol level, blood glucose levels, and WBC count. Plasma cortisol levels, plasma WBC counts, and fasting plasma blood glucose levels will be summarized by treatment group and day using descriptive statistics for observed, change from baseline, and percent change from baseline values. Summary tables will include, the arithmetic mean, standard deviation, coefficient of variation, minimum, maximum, median, and geometric means will also be reported.

[figure not shown]
7.11.2 NPRS

NPRS assessments will be done at screening, for T1 at Days 0 (baseline), 1, 2, 3, 4, 5, 8, 15, and 28. For T2, NPRS will be done at Days 0 (baseline), 1, 2, 3, 4, 5, 8, 15, and 28. Baseline for each treatment period is the NPRS score taken before the injection on Day 0.

The NPRS is an 11-point scale (0 to 10-point scale where 0 is no pain and 10 is worst pain imaginable) that allows the subject to rate the severity of their pain intensity at various points in time. The subject will use the NPRS to record their current pain, average pain in the past 24 hours, and worst pain in the past 24 hours for both their affected leg(s) and back pain. The NPRS assessments will be summarized by treatment period and day using descriptive statistics for observed, change from baseline, and percent change from baseline values.

7.11.3 BPI-SF

BPI-SF will be collected for T1 at Days 0 (baseline), 1, 2, 3, 4, 5, 8, 9, and 10. For T2, NPRS will be done at Days 0 (baseline), 1, 2, 3, 4, 5, 8, 15, and 28. Baseline for each treatment period is the BPI-SF score taken before the injection on Day 0.

The BPI-SF is a 15-item self-rating scale assessing use of medications, as well as sensory, and reactive components of pain. The BPI-SF includes items that will address components of sensory pain, including severity, location, chronicity, and degree of relief due to therapy. The BPI-SF also has items that address reactive pain components, including depression, suffering, and perceived availability of relief. The BPI-SF also has items that address reactive pain components, including depression, suffering, and perceived availability of relief. Two BFI-SF scales will be derived from the BPI-SF responses: the pain severity score and pain interference score. The two BPI-SF parameters will be summarized by treatment period and day using descriptive statistics for observed, change from baseline, and percent change from baseline values.

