3.5.2.5 Visit 8 (Treatment 1, Day 8 ± 2 days)

[Redacted text block]

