3.5.2.6 Visit 9 (Treatment 1, Day 15 ± 2 days)

[Redacted text block]

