3.5.2.7 Visit 10 (Treatment 1, Day 28 ± 2 days)

[REDACTED]

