3.5.4.5 Brief Pain Inventory - Short Form

The BPI-SF ([Appendix F](#)) is a 15-item self-rating scale assessing use of medications, as well as sensory, and reactive components of pain. The BPI-SF includes items that will address components of sensory pain, including severity, location, chronicity, and degree of relief due to therapy. The BPI-SF also has items that address reactive pain components, including depression, suffering, and perceived availability of relief. Respectable reliability has been demonstrated over short intervals using test-retest correlation; worst pain, $r=0.93$; usual pain, $r=0.78$; pain now, $r=0.59$. The BPI-SF will be collected all study visits except Screening.

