4 ENDPOINTS

4.1 Pharmacodynamic Endpoints

- Dexamethasone-induced HPA suppression as measured by:
 - Observed total blood cortisol levels, change from baseline cortisol levels, and percent change from baseline cortisol levels
 - Observed glucose levels, change from baseline glucose levels, and percent change from baseline glucose levels
 - Observed white blood cell counts, change from baseline white blood cell counts, and percent change from baseline white blood cell counts
- NPRS (average leg pain and back pain) and BPI-SF
- Change from T1 Day 0 and T2 Day 0 through Day 28 in NPRS (average leg pain and back pain) and BPI-SF over time following the index (T1) and repeat (T2) epidural injections, respectively
- Percent change from T1 Day 0 and T2 Day 0 through Day 28 in NPRS (average leg pain and back pain) and BPI-SF following the index (T1) and repeat (T2) epidural injections, respectively

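### SAP 7.11.3 ends the T1 BPI-SF schedule at Days 9 and 10, apparently visit numbers entered as days; the protocol visits and the SAP endpoint require Days 15 and 28

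*SAP*

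**What the plan says.** SAP 7.11.3, the analysis section for the BPI-SF, gives the first-period schedule as follows: "BPI-SF will be collected for T1 at Days 0 (baseline), 1, 2, 3, 4, 5, 8, 9, and 10". The next sentence gives the second-period schedule but names the other pain instrument: "For T2, NPRS will be done at Days 0 (baseline), 1, 2, 3, 4, 5, 8, 15, and 28". The section ends by saying that the two derived BPI-SF scores (severity and interference) are summarized descriptively by period and day. That sentence does not list the days.

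SAP 4.1 includes among the pharmacodynamic endpoints "Change from T1 Day 0 and T2 Day 0 through Day 28 in NPRS (average leg pain and back pain) and BPI-SF over time", with a parallel percent-change endpoint, for the index and repeat injections.

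Protocol 3.5.4.5 states: "The BPI-SF will be collected all study visits except Screening". Protocol 3.5.2.5 to 3.5.2.7 place Visits 8, 9 and 10 at T1 Days 8, 15 and 28, each with a window of ± 2 days.

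**The concern.** A SAP day list normally tells the programmer which rows to put in a by-day table. The only T1 list given for the BPI-SF contains two days on which no visit is scheduled and leaves out the two latest follow-up visits. Taken at face value, T1 would be summarized to Day 10 and T2 to Day 28, and the T1 half of the change-through-Day-28 endpoint would have no late values.

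The list could also affect data handling. SAP 7.2.5 assigns early-termination pharmacodynamic assessments to a neighbouring scheduled visit, and the protocol classes the BPI-SF as a pharmacodynamic assessment. A wrong list of scheduled days could therefore send an early-termination value to the wrong time point.

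**Working it through.** No sample size, power or error-rate figure is involved. The check compares the day lists and rebuilds the T1 list from the protocol visits.

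**Step 1. T1 list from the protocol.** T1 uses Visits 1 to 10. Dropping Screening (Visit 1), as Protocol 3.5.4.5 requires for the BPI-SF, leaves nine visits:

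| Visit | T1 day | Protocol section |
|---|---|---|
| 2 | 0 | 3.5.2.3 |
| 3 | 1 | 3.5.2.4.1 |
| 4, 5, 6, 7 | 2, 3, 4, 5 | 3.5.2.4.2 |
| 8 | 8 ± 2 | 3.5.2.5 |
| 9 | 15 ± 2 | 3.5.2.6 |
| 10 | 28 ± 2 | 3.5.2.7 |

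The BPI-SF days for T1 should therefore be 0, 1, 2, 3, 4, 5, 8, 15, 28.

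**Step 2. Compare the SAP lists.**

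| SAP list | Last three days |
|---|---|
| PD blood samples, T1 and T2 (7.11.1) | 8, 15, 28 |
| NPRS, T1 and T2 (7.11.2) | 8, 15, 28 |
| Vital signs, T1 and T2 (7.12.3) | 8, 15, 28 |
| T2 sentence within 7.11.3 | 8, 15, 28 |
| BPI-SF, T1 (7.11.3) | 8, 9, 10 |

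The NPRS sentence shows the expected form: "NPRS assessments will be done at screening, for T1 at Days 0 (baseline), 1, 2, 3, 4, 5, 8, 15, and 28".

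- In the T1 BPI-SF list but not in the protocol-derived list: {9, 10}.
- In the protocol-derived list but not in the T1 BPI-SF list: {15, 28}.
- Both lists have nine entries, which points to substitution and not to dropped visits.

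**Step 3. Could Days 9 and 10 be real assessments?** The visit windows are 8 ± 2 = Days 6 to 10, 15 ± 2 = Days 13 to 17, and 28 ± 2 = Days 26 to 30. Days 9 and 10 both lie inside the Visit 8 window. A BPI-SF completed at a late Visit 8 could fall on one of them, but it would be the Day 8 record and not a further scheduled assessment.

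**Step 4. Explanation.** The values 9 and 10 are the visit numbers for Days 15 and 28. The value 8 is both a visit number and a correct study day. Reading the last two entries as visit numbers reproduces the Step 1 list exactly. The SAP does not say that this is what happened; it is an inference.

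**Step 5. Size.** The T1 list has 9 − 1 = 8 post-baseline points, of which 2 are wrong, or 2/8 = 25%.

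**Step 6. Early-termination mapping, if the list is taken literally.** Take an early-termination BPI-SF at T1 Day 20, chosen for illustration. Under the list as written, the preceding scheduled point is Day 10, which would normally be missing, so SAP 7.2.5 would assign the value to Day 10. Under the corrected list it would go to Day 28, or to Day 15 if the Day 15 value were missing. Because 7.2.5 speaks of visits, a programmer working from the visit schedule would reach the correct result anyway.

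**The case against.** The strongest case on the other side is that nothing would actually be lost. The sentence concerns collection, and collection is governed by the protocol, which plans the BPI-SF at Visits 9 and 10. The sentence that governs the summaries names no days. SAP 4.1 and Protocol 5.2.6 both require BPI-SF change through Day 28. If 9 and 10 are visit numbers, the intended schedule is already the right one, and a programmer who found T1 data at Days 15 and 28 would probably notice the slip. The BPI-SF is also named in no primary or secondary objective: the analgesic objective rests on NPRS leg pain, and the NPRS schedule is correct.

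Most of this stands, and it limits the consequence. It does not make the list correct. It is the only T1 schedule in the SAP's BPI-SF analysis section, it conflicts with every comparable list, and the legible text of SAP section 10 declares no change to the BPI-SF schedule.

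A reader might go further and infer that the planned T1 tables omit Days 15 and 28, so that the endpoint cannot be delivered. The documents do not support that. The summary sentence sets no days, and the SAP's list of tables cannot be read in the public copy, so omission from the tables is not shown. Nor are all three of 8, 9 and 10 wrong, because Day 8 is a valid study day.

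**Conclusion.** Wrong as written, with minor severity. The T1 BPI-SF list in SAP 7.11.3 has two incorrect days out of eight post-baseline points and contradicts the protocol visits, the protocol's collection rule, the parallel SAP lists and the SAP's own endpoint. That conflict is plain on the face of the text and needs no assumption.

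The consequence is conditional. Only if the list is applied literally do the T1 summaries stop short of Day 28. Even then the data exist, and the loss is confined to descriptive tables for one pain instrument. Sample size, baseline definitions, and the AUEC28 and Emax comparison with its 80 to 125% criterion are unaffected. The reading of 9 and 10 as visit numbers is the best explanation available, but the need for correction does not depend on it.

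**What to change.** In SAP 7.11.3, change the end of the T1 day list from 8, 9 and 10 to 8, 15 and 28. In the T2 sentence that follows, replace NPRS with BPI-SF, so that the section states a BPI-SF schedule for both periods. When making the change, confirm that the BPI-SF table shells and the early-termination mapping use Days 15 and 28 for T1. The cost is a one-line text correction, with no change to design, data collection or analysis method.

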7.11.4 Area under the effect curve over 28 days and maximum effect

The area under the effect curve over 28 days (AUEC28) and maximum effect (Emax) following the T1 (index) and T2 (repeat) injections will be calculated for cortisol levels, WBC counts, and fasting blood glucose levels.

AUEC28 will be compared for cortisol following index and repeat injections within the same subject to conclude whether or not repeat injection results in more pronounced cortisol suppression. This will be done using a two-sided paired T-test with the null mean being zero.

AUEC28 and Emax will be compared for cortisol, glucose, and WBC between index injection (treatment 1) and repeat injection (treatment 2) using a mixed model analysis of variance using PROC MIXED with a fixed effect for treatment (treatment 1 and 2) and a random effect for subject. Estimates and 90% confidence intervals (CIs) will be first constructed in the logarithmic scale. The response variable will be the change from pre-dose of each PD parameter. Treatment comparisons will be performed between treatments T1 and T2 with T2 being the reference. By taking anti-logarithms, estimates and CIs for the geometric means and ratios of geometric means will be calculated. All CIs will be 2-sided.

The statistical model will have the following form:

The following SAS code will be used to run the model;

[REDACTED]

The following SAS code will be used to calculate the geometric means, geometric ratio and its confidence interval:

```
[REDACTED SAS CODE]
```

A lack of effect of repeat injection on the PD will be concluded if the 90% CIs for the ratio of T2 (repeat injection; Test) to T1 (index; Reference) for both AUEC28 days and Emax are completely contained within the range of 80 to 125%.

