7.4 Derived Variables

7.4.1 Area under the effect curve over 28 days (AUEC28)

AUEC28 days is defined as the change from baseline (for cortisol, glucose, and WBC) and calculated using linear trapezoidal summation from pre-dose to Day 28 in each treatment period.

AUEC28 analyses for the for cortisol, glucose, and WBC will be based on the assumption that the baseline assessment take place at time zero. Only scheduled and ET visit assessments will be included in the computation. If the actual time is not recorded the nominal time will be used. Cortisol, glucose, and WBC ET assessments will be mapped to Day 28 and AUEC28 will then be computed.

If a subject has no pre-dose value, AUEC28 will not be calculated. In the case where a subject has two values recorded at the same time, the two scores will be averaged.

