7.4.2 Maximum Effect (Emax)

Emax is the maximum increase from baseline (pre-treatment level, T1 or T2) in glucose level and WBC count or the maximum decrease in cortisol levels over the 28 days post dose in each treatment period. An Emax value will be calculated for cortisol, glucose, and WBC for each treatment period (T1/T2).

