10 CHANGES TO PLANNED PROTOCOL ANALYSIS

In the protocol, it is stated that: “No formal statistical hypothesis testing will be performed in this study, however descriptive statistics will be presented”. However, given that inferential analysis will be carried out on the PD data, this statement is disregarded.

[Redacted]	[Redacted] [Redacted] [Redacted]	■	
[Redacted]	[Redacted]seline [Redacted] [Redacted]	■	
[Redacted]	[Redacted] [Redacted] [Redacted]	■	

[REDACTED]	[REDACTED]	[REDACTED]	

[REDACTED]	[REDACTED]	[REDACTED]	

[REDACTED]	[REDACTED]	[REDACTED]	[REDACTED]
[REDACTED]	[REDACTED]	[REDACTED]	[REDACTED]
[REDACTED]	[REDACTED]	[REDACTED]	

[REDACTED]	[REDACTED]	■	

[REDACTED]	[REDACTED]	[REDACTED]	[REDACTED]
[REDACTED]	[REDACTED]	[REDACTED]	[REDACTED]
[REDACTED]	[REDACTED]	■

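### AUEC28 is a signed area of change from baseline but is compared in logs: under net suppression the cortisol ratio cannot be computed from the readable text, and no rule covers areas at or below zero for any marker

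*SAP*

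**What the plan says.** SAP 7.4.1 defines the parameter: "AUEC28 days is defined as the change from baseline (for cortisol, glucose, and WBC) and calculated using linear trapezoidal summation". It runs from pre-dose to Day 28 in each period, and protocol 5.2.7 gives the same definition. Neither gives a direction for cortisol. SAP 7.4.2 does so for Emax, which takes the largest rise for glucose and WBC "or the maximum decrease in cortisol levels over the 28 days post dose in each treatment period".

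On scale, SAP 7.11 says: "All comparisons between treatments will be analyzed in log scale but will be reported as ratios". SAP 7.11.4 and protocol 5.2.7 fit a mixed model (treatment fixed, subject random), build 90% intervals in logs and back-transform to geometric means and their ratio. The response is the change from pre-dose ("constructed in the logarithmic scale. The response variable will be the change from pre-dose of each PD parameter"). Lack of effect of the repeat injection is concluded only if the T2/T1 intervals for both AUEC28 and Emax lie within 80-125%.

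For cortisol, SAP 7.11.4 also compares the two areas within subject "to conclude whether or not repeat injection results in more pronounced cortisol suppression". The method is given as: "This will be done using a two-sided paired T-test with the null mean being zero". No scale is named for this test.

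The handling rules in SAP 7.4.1 cover missing times, duplicate values, early-termination visits and a missing baseline ("If a subject has no pre-dose value, AUEC28 will not be calculated"). They say nothing about an area of zero or less. SAP section 10 sets aside the protocol's statement that no formal testing will be done: "given that inferential analysis will be carried out on the PD data, this statement is disregarded". The model equation and SAS code in SAP 7.11.4 are not readable.

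**The concern.** The drug is expected to lower cortisol, so change from baseline is mainly negative, and so is its area. A geometric mean ratio needs strictly positive inputs. The parameter and the scale therefore do not fit together for the one marker that SAP 7.11.4 singles out.

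Glucose and WBC are expected to rise, so their sign is not the difficulty. But a brief rise is spread over a 27-day area measured against a single pre-dose sample, and noise alone can push that area to zero or below. The same holds for cortisol once its sign is reversed.

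What is exposed is the inferential PD comparison that SAP section 10 says will be carried out. If undefined logs are left as missing, subjects drop out according to their own outcome. If the choice waits until data are seen, then dropping, shifting, taking absolute values and reversing the sign are all open, and they can give different answers.

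**Working it through.** **Step 1. The definitional point, with no assumed effect size.** Area = Σ wᵢ(yᵢ − y₀). If the weighted change is negative (net suppression), log(area) does not exist. The plan states no expected area, SD or power, so there is no figure of its own to reproduce.

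**Step 2. Weights.** Protocol 3.5.4.1 samples at Visits 3 to 10 in T1. That is Day 1 pre-dose and Days 2, 3, 4, 5, 8, 15 and 28, or t = 0, 1, 2, 3, 4, 7, 14, 27 days. SAP 7.11.1 lists Day 1 as well as pre-dose; I take them as one sample. The trapezoid weights are 0.5, 1, 1, 1, 2, 5, 10, 6.5 (sum 27).
- Days 8, 15 and 28 carry (5 + 10 + 6.5)/27 = 79.6%.
- The pre-dose value is subtracted at every point, so its net weight is 0.5 − 27 = −26.5.

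**Step 3. Assumed profiles** (none is in the readable documents). Effect as % of baseline on Days 2/3/4/5/8/15/28:
- cortisol long 80/80/80/70/50/20/0: 80 + 80 + 80 + 140 + 250 + 200 = 830 %-days
- cortisol middle 80/70/50/30/10/0/0: 80 + 70 + 50 + 60 + 50 = 310
- cortisol short 70/30, then 0: 100
- glucose +20/+5, then 0: 25
- WBC +50/+20/+5, then 0: 75

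Samples are independent mean-one lognormal values with within-subject CV 5-30%. There are 12 subjects, hence 24 areas per marker.

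**Step 4. Check by hand.** Middle cortisol, CV 10%: weight × expected level (baseline = 1) is 26.5, 0.2, 0.3, 0.5, 1.4, 4.5, 10, 6.5. The root sum of squares is √867.1 = 29.4, so the SD is 29.4 × 10 = 294 %-days. Then 310/294 = 1.05, and a normal approximation gives 14.6% of areas ≤ 0. Simulation gives 14.3%.

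**Step 5. Share of areas ≤ 0 after reversing the cortisol sign (%).**

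| CV | long | middle | short | glucose | WBC |
|---|---|---|---|---|---|
| 5% | 0 | 1.5 | 25 | 43 | 30 |
| 10% | 0.07 | 14.3 | 38 | 45 | 39 |
| 15% | 1.7 | 24.7 | 43 | 46 | 41 |
| 20% | 5.7 | 31.2 | 46 | 46 | 42 |
| 30% | 15.4 | 38.8 | 49 | 45 | 43 |

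Without sign reversal the cortisol areas with no log are the complement: 100 to 84.6% (long) and 98.5 to 61.2% (middle). With within-period correlation of 0.5 the reversed shares are lower: long 0-6.7%, middle 0.1-32%, short 17-46%, glucose 40-46%, WBC 23-43%. Larger assumed rises (glucose 45, WBC 114 %-days, additive normal noise) give 38-48% and 22-45%.

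**Step 6. At least one of 24 areas ≤ 0**, 1 − (1 − p)²⁴: long 0, 1.5, 33, 76, 98% of trials over the five CVs; middle 30, 98, then about 100%; glucose and WBC about 100%.

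**Step 7. True T2/T1 = 1.5, sign reversed, undefined logs dropped.** T2 profiles: long 90/90/90/85/75/43/0 (1245 = 1.5 × 830); middle 90/80/65/50/26/0/0 (465 = 1.5 × 310).
- Long: estimates 1.51, 1.57, 1.63, 1.58, 1.38, with 24.0 falling to 21.7 of 24 records kept.
- Middle: 1.60, 1.39, 1.24, 1.17, 1.08, with 23.8 falling to 15.5 kept.
- The 80-125% rule is met in at most about 0.1% of trials in any of these scenarios.

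**Step 8. Original scale, all 12 subjects kept, middle profile.** Mean T2−T1 difference 153-157 (true value 465 − 310 = 155); 90% interval coverage 90%; half-width 104, 209, 311, 416, 623 %-days over the five CVs.

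**Step 9. Emax.** Values ≤ 0 are uncommon: cortisol 0-0.1%, glucose 0.4-10%, WBC 0-5.8%. The log ratio is workable there.

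**The case against.** **Redaction.** The model form and both code blocks are hidden exactly where a sign change or a rule for missing logs would sit. This stands. The claim is limited to the readable text, and checking the code comes first. But a sign change found only in code would still need stating in SAP 7.4.1.

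**The intended sign is obvious.** The parameter is an area under an effect curve, the effect is suppression, and cortisol Emax is already a decrease, so one clarifying line makes net-suppressed areas positive. This is largely right for a long effect with low noise: at CV 5% no area in the long profile is lost. It does not help with areas still ≤ 0, or with glucose and WBC, where the sign was never the trouble.

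**No wrong decision is shown.** A reader might infer that dropping records would produce false conclusions of no effect, because the middle-profile estimate moves toward 1. The calculations do not support that: at a true ratio of 1.5 the rule is met in about 0.1% of trials at most, because the intervals are wide. In the long profile the estimate lies above 1.5 up to CV 20%. Nor do the documents say that undefined logs would be dropped.

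**The log scale is blamed for low pass rates.** It should not be. At a true ratio of 1, long profile, CV 10%, the rule is met in 4.5% of trials on the log scale and in 6.7% with a raw-scale margin of −20%/+25% of the mean area. Twelve subjects and a noisy area explain that.

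**Thin assumptions.** The tabulated glucose and WBC figures each rest on one assumed profile. The larger rises in step 5 do not remove the problem, but the exact rates should not be relied on.

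**Conclusion.** The point holds for the readable text. A negative cortisol area has no log, so under net suppression half of the cortisol decision rule cannot be evaluated as written. That follows from the definitions alone. The absence of any rule for areas ≤ 0 is a second gap, affecting all three markers. How often it bites depends on effect size, duration and noise that the readable documents do not give: under the assumptions above, from never (long cortisol effect, CV 5%) to nearly half of areas (short cortisol effect, glucose).

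The harm shown is subjects lost by outcome and a distorted ratio if undefined logs are dropped, not a raised rate of false conclusions. Descriptive summaries, which serve the primary objective of characterizing PD, are unaffected, as is a paired t-test on raw areas. It should be fixed before database lock, because the only stated decision rule for the PD comparison depends on it.

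**What to change.** First check the redacted model form and code for a sign change or a rule for areas ≤ 0. Then, before database lock, amend SAP 7.4.1, 7.11 and 7.11.4, record the change in SAP section 10, and align protocol 5.2.7 if it is amended:

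- (a) Define the cortisol effect for AUEC28 as baseline minus observed, matching Emax.
- (b) For all three markers, add an original-scale analysis of signed AUEC28 with the same mixed model. Keep every subject, including areas ≤ 0, and report the T2−T1 difference with its 90% interval.
- (c) State that the cortisol paired t-test uses these raw areas, and exempt both original-scale analyses from the general log-scale sentence in SAP 7.11.
- (d) Keep the stated log-scale mixed model as the estimator for the 80-125% AUEC28 ratio when every area of that marker is above zero. Otherwise drop nothing silently: count and list areas ≤ 0 by marker and period, report the ratio criterion as not evaluable for that marker, and rely on the original-scale difference. Any difference margin is for the sponsor to set before lock.
- (e) Keep the log ratio for Emax as a positive magnitude, and list any Emax ≤ 0.

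The cost is wording and a few lines of code, with no new data. The price is precision and availability. With 12 subjects the raw-scale half-width is 104-623 against a T1 area of 310 %-days in the middle profile, where the paired t-test detects a true ratio of 1.5 in 64, 22, 12, 9 and 7% of trials over the five CVs (100 down to 19% in the long profile). Under (d), the AUEC28 ratio conclusion may often be unavailable, especially for glucose and WBC.
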